This study is a **randomized control trial**, in which patients and treating physicians will be blinded, designed to test whether itraconazole after surgery in fungal sensitive, fungal culture positive CRSwNP patients will have decreased rates of nasal polyp recurrence as compared to placebo treated patients (Figure 1). **The study population will come from the rhinology practice of the Department of Otorhinolaryngology where 3 rhinologists practice** (Drs. [name], [name], and [name]) as well as the rhinology practices at UTSW and UTSA. Among the 3 rhinologists of UT Houston, approximately 150 sinus surgeries are scheduled annually involving CRSwNP. Definitions of CRSwNP are based on the criteria outlined by The Rhinosinusitis Initiative[6]. Inclusion and exclusion criteria are listed in Table 1. Up to 500 CRSwNP patients undergoing a medically-indicated sinus surgery over 3-4 years will be screened and recruited to undergo peripheral blood draw that will be used in an *in vitro* ELISpot assay to identify those that are fungal sensitive. Blood from UTSA and UTSW will be shipped to UT Houston for processing. We anticipate that 80% of those screened patients will meet inclusion criteria allowing us to enroll about 400 CRSwNP patients undergoing sinus surgery. After surgery, patients will be randomized into 1 of 2 groups (1:1 ratio, stratified by presence of asthma): 1) oral itraconazole (200 mg q12 hrs) or 2) placebo for 24 weeks. Patients will be evaluated in the clinic on post-treatment weeks 2 ( $\pm$  1 week), 6 ( $\pm$  2 weeks), 12 ( $\pm$  2 weeks), and 24 ( $\pm$  3 weeks) as per the typical post-operative management protocol (Figure 2). Patients will be clinically followed for an additional 24 weeks post-treatment for recurrent nasal polyps. Therefore, patients will be followed for a total of 48 weeks after sinus surgery or until recurrent nasal polyps requiring treatment are noted.

It is current standard practice for all CRS patients to complete validated health assessment questionnaires for CRS (SNOT-22) and undergo recorded nasal endoscopic exams at each clinic visit. All medications and any treatment side effects will be recorded at each clinic visit.

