Blood will be drawn on the day of surgery for the ELISpot assay and for a baseline hepatic function. Medication compliance will be assessed by counting remaining pills at each follow-up visit. A small amount of diseased ethmoid tissue at time of surgery and post-treatment (either at time of recurrent nasal polyps or completion of 24 week treatment) will be obtained and analyzed by microarray for subjects enrolled at the UT Houston site. Sinus secretions will be sampled from the ethmoid sinus cavity at time of surgery and at clinic visit when study medication is stopped for subjects enrolled at the UT Houston site.

[figure not shown]
**Study endpoints:** The primary efficacy endpoint is recurrence of nasal polyps requiring medical intervention over 48 weeks post-surgery. Nasal endoscopy will evaluate for recurrent nasal polyps and will be scored using a nasal endoscopy scoring system. Intervention for recurrent nasal polyps with prednisone will be determined clinically by the blinded treating physician. The secondary endpoints will be validated health assessment scores (SNOT-22) for CRS, nasal endoscopy scores, and qualitative and quantitative fungal cultures.

The safety endpoints will include possible adverse events associated with itraconazole (e.g., EKG changes shortness of breath, and anaphylactic reactions to itraconazole or intolerable side effects requiring the patient to stop study medication).

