**Treatment blinding and randomization protocol:** Itraconazole tablets (200 mg) will be purchased from the manufacturer. Itraconazole 200 mg tablets will be crushed and compounded into a de-identified capsule; matching placebo capsules containing cellulose which will be prepared with good manufacturing practice (GMP) standard (Avicel; FMC BioPolymer, Philadelphia, PA) by Hope Compounding Pharmacy. Each volunteer will take 1 capsules, corresponding to 200 mg of itraconazole or placebo, twice daily. Patients will be stratified by presence of asthma as determined by history and positive pulmonary function test or methacholine challenge test. A randomization schedule using permuted blocks and stratified by presence/absence of asthma will be prepared using a computer-generated random number sequence. Allocation concealment will be achieved using opaque, sealed, sequentially numbered envelopes which will be held by the research coordinator in a locked filing cabinet. A calculated number of 24 weeks of itraconazole or placebo will be dispensed in prepackaged 30-day supply boxes by the Hope Compounding Pharmacy and distributed by the Research Coordinator.

Itraconazole or placebo will be taken with either orange juice, 8 ounces of cola beverage or full meal to maximize oral absorption. Since prescribed proton pump inhibitors or H2-antagonist can interfere with itraconazole absorption, these medications will be taken midday if needed.

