## Statistics

### Power analysis

This is a pilot study focused on estimating a range of plausible treatment effects. We anticipate enrolling **500 patients over a 3-4 year period** with an anticipated 15% dropout rate. A total of 340 subjects should

Table 2

Recurrence Rates		Power	Power
Placebo	Treatment	N=320	N=102
50%	20%	1.00	0.86
50%	25%	0.99	0.68
50%	30%	0.93	0.46
50%	35%	0.61	0.26

be available for final analyses. However, we also performed a power analysis should the number of possible patients be as low as 120 patients over the 3 years with similar 15% drop rate for possible N=102. Although the goal of this study is to estimate an unbiased treatment effect, we calculated power (Table 2) to detect a range of effect sizes (as reported in the literature) assuming a two-sided test with alpha of 0.05 and N=320 and 102. The study would have adequate power to detect a large effect size. The planned complementary Bayesian analyses will provide probabilities of clinically important treatment benefits to guide the conduct of future trials.

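### Randomisation is stratified by asthma, but the Statistics section names no primary analysis and uses asthma in none; if asthma predicts recurrence, an unstratified analysis loses some precision and power

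*Combined protocol and SAP*

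**What the plan says.** Study Design sets the allocation: "patients will be randomized into 1 of 2 groups (1:1 ratio, stratified by presence of asthma". Its paragraph on treatment blinding and randomization adds "A randomization schedule using permuted blocks and stratified by presence/absence of asthma" and says how asthma is established (history plus a positive pulmonary function or methacholine test). Study Procedures repeats the stratification. No other stratification factor is named.

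The endpoint is also in Study Design: "The primary efficacy endpoint is recurrence of nasal polyps requiring medical intervention over 48 weeks post-surgery".

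The Statistics section consists of the power analysis. Its only description of a test is "assuming a two-sided test with alpha of 0.05 and N=320 and 102". Table 2 lists recurrence rates (placebo, treatment) and power at N=320 and N=102: "50% 20% 1.00 0.86", "50% 25% 0.99 0.68", "50% 30% 0.93 0.46", "50% 35% 0.61 0.26". Complementary Bayesian analyses are promised without a model. Asthma is not mentioned anywhere in the section.

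**The concern.** Stratified allocation balances asthma between the arms, so differences in recurrence between asthmatic and non-asthmatic patients add nothing to the sampling error of the treatment comparison. An analysis that ignores the strata still counts those differences in its standard error. If asthma predicts recurrence, the confidence interval is then wider than the design warrants and the test gives up some power.

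Precision matters here because the section describes a pilot whose aim is to estimate the treatment effect, and because it allows for as few as 102 evaluable patients. In addition, with no analysis named, the choice between an asthma-adjusted and an unadjusted result could be made after the data are seen.

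**Working it through.** **1. What calculation lies behind Table 2?** Inputs from the Power analysis: two-sided alpha 0.05, placebo rate 50%, treatment rates 20, 25, 30 and 35%, totals of 320 and 102. With 1:1 allocation, n = 160 or 51 per arm. For an unstratified two-proportion test with continuity correction,

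power = Φ{ [ |p1−p2| − 1/n − 1.96·√(2p̄(1−p̄)/n) ] / √[(p1(1−p1)+p2(1−p2))/n] }, where p̄ is the mean of p1 and p2.

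- n=51, 50% vs 20%: (0.3000 − 0.0196 − 0.1851)/0.0897 = 1.06, power 0.856.
- n=160, 50% vs 35%: (0.1500 − 0.0063 − 0.1083)/0.0546 = 0.648, power 0.742.

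| Placebo vs treatment | N=320 stated | N=320 recomputed | N=102 stated | N=102 recomputed |
|---|---|---|---|---|
| 50% vs 20% | 1.00 | 1.000 | 0.86 | 0.856 |
| 50% vs 25% | 0.99 | 0.996 | 0.68 | 0.677 |
| 50% vs 30% | 0.93 | 0.946 | 0.46 | 0.459 |
| 50% vs 35% | 0.61 | 0.742 | 0.26 | 0.263 |

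The N=102 column matches to rounding, and three N=320 cells agree within 2 points. The 0.61 cell does not reproduce. Other versions at N=320 give 0.777 (no correction), 0.784 (unpooled), 0.778 (arcsine), 0.738 (Fisher) and 0.860 (one-sided). That cell needs a separate check.

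**2. What ignoring asthma does to the standard error.** Assumptions not in the documents: half the patients have asthma, overall recurrence is 50% in both arms, and the asthma-recurrence odds ratio (OR) takes the values shown. The stratum rates are then p and 1−p with p = √OR/(1+√OR). The variance left within strata is p(1−p), against 0.25 in the unstratified formula. The large-sample type I error of the unstratified test is 2{1 − Φ(1.96/r)}, with r = √[p(1−p)/0.25].

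| OR | Stratum rates | p(1−p) | r | Interval too wide by (1/r − 1) | Type I error |
|---|---|---|---|---|---|
| 1 | 50% / 50% | 0.250 | 1.000 | 0% | 5.0% |
| 2 | 41% / 59% | 0.243 | 0.985 | 1.5% | 4.7% |
| 3 | 37% / 63% | 0.232 | 0.963 | 3.8% | 4.2% |
| 5 | 31% / 69% | 0.214 | 0.924 | 8.2% | 3.4% |

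**3. Simulation.** 200,000 trials per cell, permuted blocks of 4 within strata (block size assumed), a common treatment odds ratio across strata, and marginal rates as in Table 2.

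Type I error of the uncorrected unstratified test at OR 1, 2, 3 and 5:

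- N=320: 0.050, 0.046, 0.042, 0.034. The Cochran-Mantel-Haenszel (CMH) test stays at 0.048 to 0.050.
- N=340: about 4% at OR 2 to 3 and about 3% at OR 5.
- N=102: 0.060, 0.055, 0.050, 0.042. It falls below 5% only from an OR of about 3.

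Power, unstratified → CMH, both continuity-corrected as Table 2 appears to be:

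| OR | N=320, 50% vs 35% | N=102, 50% vs 30% |
|---|---|---|
| 1 | 0.739 → 0.739 | 0.480 → 0.474 |
| 2 | 0.742 → 0.753 | 0.480 → 0.481 |
| 3 | 0.744 → 0.771 | 0.478 → 0.489 |
| 5 | 0.755 → 0.803 | 0.478 → 0.515 |

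With 30% asthma prevalence the gains are similar: 0.749 → 0.793 and 0.478 → 0.510 at OR 5. Where power is already near 1, as for 50% vs 20% at N=320, there is little to gain. The largest loss from stratifying is at N=102 with no asthma effect: 0.283 → 0.275 for 50% vs 35%.

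**The case against.** A reader might infer from Table 2 that the plan prescribes an unstratified two-proportion test. The documents do not support that. No test is named, and simple two-proportion sizing is common even when a stratified analysis is intended. One cell of the table also fits no version tried. The defect is an omission, not a wrong choice of test.

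A reader might also infer that the analysis is certain to be conservative and to lose much power. That needs an asthma effect, and the documents give none. Large gaps appear only when asthma is very strongly prognostic. Stratum recurrence of 25% and 75% (OR 9) gives power of 0.84 against about 0.90 at N=340 for 50% vs 35%, and 0.55 against about 0.65 at N of about 100 for 50% vs 30%, without continuity correction. At 40% and 60% (OR 2.25) the same comparisons show a difference of about 1 point or none.

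Nor is conservatism shown at the small sample size: at N=102 the uncorrected unstratified test is slightly above 5% for odds ratios up to 2. With the continuity correction, type I error at N=320 is already 0.038 with no asthma effect, and that shortfall comes from the correction, not from ignoring strata.

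Finally, this is a pilot aimed at estimation, so power is secondary. These objections limit the size of the point. They leave standing that the stratification factor is carried into no analysis and that the primary analysis is undefined.

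**Conclusion.** The point holds as an omission with a conditional and mostly modest cost. Asthma governs the randomisation, the Statistics section does not use it, and the only calculation there is consistent, in seven of eight cells, with an unstratified comparison.

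With half the patients asthmatic, stratifying would add nothing if asthma has no effect, about 1 point of power or less for an odds ratio up to about 2, about 1 to 3 points at 3, and about 3 to 5 points at 5. These figures are for 50% vs 35% at N=320 and 50% vs 30% at N=102. Large-sample intervals would be about 1.5%, 4% and 8% too wide at odds ratios of 2, 3 and 5. Asthma prevalence, its effect and the block size are all assumptions.

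The case for acting rests as much on settling the primary analysis in advance as on the power gained.

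**What to change.** In the Statistics section, name the primary analysis and state that it is stratified by asthma as recorded at randomisation. For recurrence as a binary outcome over 48 weeks, use a CMH test with the Mantel-Haenszel risk difference and its 95% CI. If time to recurrence is analysed instead, use a log-rank or Cox analysis stratified by asthma. Include the same asthma term in the Bayesian model. Separately, recheck the 0.61 entry in Table 2.

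The cost is a sentence or two. Asthma status is already collected for randomisation, so no new data are needed. The statistical downside is at most about 1 point of power at N=102 if asthma turns out to have no effect.

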**Figure 1.**

**Figure 2.**

[figure not shown]

TABLE 1	
Inclusion	
 
18-75 years old, Sinus symptoms for <math>\geq</math>12 weeks and nasal polyps noted on nasal endoscopy or CT, undergoing medically-indicated sinus surgery for CRS
 
Nasal polyps noted at time of surgery
 
Positive ELISpot assay and evidence of fungi within diseased sinus cavities
 

Exclusion	Pregnant, Autoimmune disease, cystic fibrosis, Aspirin exacerbated respiratory disease, chronic disease such as uncontrolled diabetes, cancer or HIV, history of liver or kidney disease that have effects on immune system

## **AIM 2**

**To determine the effect of post-operative oral itraconazole on gene expression linked to CRS inflammation and to identify genes whose expression may serve as predictive biomarker for positive clinical response by microarray.** This analysis will only be performed for subjects enrolled at the UT Houston site.

Diseased ethmoid sinus tissue before and after treatment or at time of recurrent nasal polyps will be analyzed by microarray analysis. Basically, a small amount of diseased ethmoid tissue will be taken at the time of surgery and again at the end of 24 weeks or at time of nasal polyp recurrence. Only a small amount of tissue, approximately 3 mm squared area of tissue is needed to extract the 100 ng of total RNA needed for microarray analysis. The collected tissue will be quick frozen in liquid nitrogen and stored at -80C. Then, RNA will be isolated from the tissue and assessed for quality.

One hundred nanograms of total RNA will be amplified on an ArrayPlex (Beckman Coulter, Inc., Brea, CA) using the Ovation® RNA Amplification System V2 and WB reagent (Nugen, Inc., San Carlos, CA). Of the amplified cDNA, 4.4  $\mu$ g will be labeled using the FL Ovation™ cDNA Biotin Module V2 (Nugen, Inc.) according to the manufacturer's recommendations. The labeled cDNA will be hybridized onto

Affymetrix human genome HT HG-U133+ PM arrays (Affymetrix, Santa Clara, CA) and processed according to Affymetrix technical protocols.

The data will be expressed as normalized gene expression levels and pictorially can be expressed on a heat map to show up or down regulated genes between patient groups (i.e. patients treated with itraconazole that do not develop recurrence of nasal polyps as compared to placebo treated patients that develop recurrent nasal polyps, etc).

## **Study Population**

### Recruitment of human subjects

For these studies, CRSwNP patients aged between 18 to 75 years of age scheduled for medically indicated sinus surgery will be recruited from the Otorhinolaryngology clinics associated with UT Houston Medical School, UT Southwestern Medical School and UT San Antonio Medical School. CRSwNP patients meeting inclusion and exclusion criteria who are undergoing clinical evaluation by the investigators will be approached for enrollment into the study (see Table 1).

*Inclusion:* Definitions of CRSwNP are based on the criteria outlined by The Rhinosinusitis Initiative[5]. All CRSwNP patients will have had 2 or more sinonasal symptoms for longer than 12 weeks and nasal endoscopic exam and/or CT imaging results consistent with paranasal sinus inflammation and nasal polyposis.

*Exclusion:* Patients with cystic fibrosis or aspirin exacerbated respiratory disease will be excluded. Pregnant women, patients who have smoked in the last month, subjects with a co-morbid disease that can alter their immune system such as uncontrolled diabetes , cancer, or an immunodeficiency, or subjects with known pulmonary disease other than asthma will be excluded as these conditions may affect the immune system and/or pulmonary physiology. In addition, patients with pre-existing liver, congestive heart failure, known EKG abnormalities, or any disease or allergy preventing patient from taking itraconazole will be excluded.

To screen for ventricular dysfunction, study candidates will be asked about history of orthopnea, paroxysmal nocturnal dyspnea, dyspnea on exertion with routine activities and changes in exercise tolerance over the previous year.

A baseline EKG and hepatic function panel will be required.

## **Study Procedures**

### EKG

Enrolled patients who respond negative to all screening questions about ventricular dysfunction will undergo a baseline EKG. Only those patients with normal EKGs, no evidence of ST changes or prolonged Q-T interval, will be able to participate in the study. The EKG will be performed before any study medication is dispensed.

A baseline EKG will be required. A follow-up EKG will be performed at each follow up visit.

### Peripheral Blood Draw

No more than fifty milliliters (about 3 tablespoons) of venous blood will be drawn on any one day. This is a relatively small amount and is not associated with hypovolemia or anemia. For comparison, approximately 500 ml of blood is drawn for blood drives.

The blood on the initial blood draw will be used to isolate peripheral blood mononuclear cells. These cells will be analyzed by an *in vitro* ELISpot assay to determine if patients have memory to a panel of fungal antigens commonly found in diseased sinuses. Those with positive ELISpot assays, meaning evidence of immune memory to common fungal antigens, will be eligible for randomization into either itraconazole or placebo group. Blood collected on the day of surgery will also be used to measure baseline liver enzyme levels. At week 24, an extra vial of no more than 8.5 mL will be drawn to assess inflammatory markers after treatment course.

**Medically-Indicated Endoscopic Sinus Surgery with collection of diseased sinus tissue and sinus swab (for subjects enrolled at the UT Houston site)**

Recruited patients will be CRSwNP patients that are scheduled for medically-indicated sinus surgery. Diseased sinus tissue and nasal polyps are removed as a part of the surgery. A portion of diseased ethmoid tissue will be collected and stored at -80C for later processing.

After initial polypectomy to expose some of the sinus cavity, a swab of the sinus cavity will be collected. This sample will be collected and processed for PCR analysis to quantitate and speciate fungal microbiome. No additional risk to the patient is incurred with either tissue or sinus swab collection.

**Randomized into itraconazole versus placebo group**

Patients with positive ELISpot assay (indicating fungal immune sensitivity) will be stratified based on asthma and randomized as described above. The Hope Compounding Pharmacy will distribute the appropriate drug to patients in 30-day supply boxed in de-identified pills. The patient randomization list will be kept stored and secured within the Otorhinolaryngology research offices.

Itraconazole is an oral antifungal that can cause adverse reactions. Itraconazole is clinically used routinely for treatment of nail fungus and other fungal diseases. All enrolled patients will be asked about history of congestive heart failure, liver disease, alcohol consumption history, shortness of breath, skin reactions, hearing loss, nerve pain, nausea, vomiting, diarrhea, headaches, chest pain, current medications and any psychological symptoms. In addition, liver function will be measured at baseline before subjects begin their treatment course. With itraconazole, the FDA only recommends routine liver function monitoring in patients with preexisting hepatic function abnormalities. Patients with hepatic disease or elevated liver enzymes at baseline will be excluded from the study.

**Monitored post-operative by nasal endoscopy, subjective symptoms, adverse reactions, and collection of ethmoid tissue**

As noted in Figure 2, patients will be seen for routine post-operative clinic visits as per typical post-operative standardized care. During these clinic visits, patients routinely undergo review of sinus symptoms, health, medication, and nasal endoscopy and complete health assessment questionnaires. In addition, patients will be asked about any specific adverse events commonly associated with itraconazole as noted above.

For those noted to have recurrent nasal polyps requiring medical intervention, a small biopsy of ethmoid diseased sinusal polyp mucosa will be obtained and stored at -80C for microarray analysis.

For those without recurrent nasal polyps, a small biopsy of ethmoid sinusal mucosa will be obtained and stored at -80C for microarray analysis at post-treatment week 24.

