Despite sinus surgery, many CRSwNP patients experience recurrence of nasal polyps. There remains no clear consensus of the appropriate post-operative treatment to minimize this recurrence. Approximately 40-70% of CRSwNP patients experience recurrent nasal polyps within 1 year after surgery even with the current post-operative medical management including an extended course of oral steroids, antibiotics and saline irrigations. Using a peripheral blood based ELISpot assay evaluating Th2 cell memory for fungal antigens, we are able to identify CRSwNP patients with fungal sensitivity. **We hypothesize that this CRSwNP subtype will demonstrate positive clinical effects with post-operative itraconazole on nasal polyp recurrence rates and health status assessment.**

**Aim 2.** Determine the effect of post-operative oral itraconazole on gene expression linked to CRS inflammation and to identify genes whose expression may serve as predictive biomarker for positive clinical response to itraconazole by microarray analysis. In preliminary studies, ST2 and other genes were significantly elevated in inflamed sinonasal mucosa from CRSwNP patients as compared to healthy

controls. **We hypothesize that the expression of a number of genes will be affected by treatment of oral itraconazole after sinus surgery and expression of some genes may correlate with a positive clinical response to itraconazole.**

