**Biopsy of ethmoid sinus tissue (for subjects enrolled at the UT Houston site)**

As a part of medically indicated sinus surgery, diseased ethmoid sinonal tissue is removed and a small amount of this tissue will be collected for microarray analysis. The remainder of the tissue will be sent to pathology per routine.

At the time of nasal polyp recurrence or at post-treatment week 24, a small biopsy of ethmoid sinus tissue will be collected. First the site will be topically anesthetized by spraying the nasal and sinus cavity with 1% lidocaine. This is typically done prior to nasal endoscopy which all CRS patients undergo during routine clinic visit. Then, a lidocaine soaked cotton ball will be applied to the biopsy site which will be the posterior medial wall of maxillary antrostomy, for about 5 minutes. After that elapsed time period, endoscopic thru-cutting instrument will be used to obtain a biopsy of ethmoid sinus tissue, approximately 3 mm squared area. Topical afrin will be applied to biopsy site for hemostasis. The collected tissue will be stored at -80C and processed to extract RNA for microarray analysis.

In addition, a swab of the sinuses will be collected and processed for PCR analysis to quantitate and speciate fungal microbiome after treatment.

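### The Aim 2 post-treatment biopsy depends on outcome in tissue type and timing, so the protocol's example gene-expression contrast cannot show drug action on sinus mucosa

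*Combined protocol and SAP*

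**What the plan says.** Aim 2 (Objectives) has two parts. The first is to "Determine the effect of post-operative oral itraconazole on gene expression linked to CRS inflammation"; the second is to find genes that predict response. Both are limited to the Houston site.

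The protocol describes the specimens in several places:

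- **At surgery** (Study Procedures, surgery and tissue collection): "A portion of diseased ethmoid tissue will be collected and stored at -80C for later processing".
- **After surgery, recurrence** (Study Procedures, post-operative monitoring): "For those noted to have recurrent nasal polyps requiring medical intervention, a small biopsy of ethmoid diseased sinusal polyp mucosa will be obtained".
- **After surgery, no recurrence** (same section): "For those without recurrent nasal polyps, a small biopsy of ethmoid sinusal mucosa will be obtained", at week 24.
- **Timing** (Study Design): "either at time of recurrent nasal polyps or completion of 24 week treatment". The biopsy section repeats it: "At the time of nasal polyp recurrence or at post-treatment week 24, a small biopsy of ethmoid sinus tissue will be collected".
- **Site** (biopsy section): lidocaine is applied to "the biopsy site which will be the posterior medial wall of maxillary antrostomy". This holds for all clinic biopsies, and the sample is still called ethmoid.

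The Aim 2 section specifies no model and no adjustment for tissue type or biopsy time. Its one illustration compares itraconazole patients who stay free of recurrence with placebo patients who recur.

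**The concern.** If the monitoring section is followed, every specimen taken at recurrence is polyp and every specimen from a patient without recurrence is not. Tissue type and outcome then coincide. Covariate adjustment cannot separate them afterwards, because no patient who recurs supplies non-polyp mucosa and no patient without recurrence supplies polyp. The remedy has to be made at collection.

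Biopsy time follows outcome as well: an early recurrence is sampled after a short time on drug, and a patient without recurrence at about week 24. Change from surgery has the same weakness, since the surgical specimen is compared later with polyp in some patients and with non-polyp mucosa in others.

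Late recurrence is left open. Follow-up runs to 48 weeks. A patient clear at week 24 who recurs afterwards meets the week-24 rule and then the recurrence rule, which has no time limit. The protocol does not say which specimen is analysed.

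What is at stake is the first half of Aim 2. A gene list could be reported as the effect of itraconazole on inflamed mucosa when it reflects the difference between polyp and mucosa.

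**Working it through.** The documents give no sample size, power or error rate for Aim 2, so there is no figure of the plan's to reproduce. The check asks how much apparent arm difference arises from tissue mix alone.

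**Inputs**

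- Recurrence rates from Table 2 (Power analysis): placebo 50%; itraconazole 20%, 25%, 30% or 35%.
- Treatment 24 weeks, follow-up 48 weeks (Study Design).
- D, the mean polyp-minus-mucosa difference for a gene: not in the documents. Results are given as multiples of D.

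**Formula.** For a gene on which the drug has no direct action:

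apparent difference = (polyp share in group A − polyp share in group B) × D

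**1. The illustrated contrast.** All specimens in the placebo-with-recurrence group are polyp, and none in the itraconazole-without-recurrence group are. The difference is (1 − 0) × D = D.

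**2. All randomised patients by arm, every 48-week recurrence biopsied as polyp.**

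- 50% vs 20%: 0.50 − 0.20 = 0.30 D
- 50% vs 35%: 0.50 − 0.35 = 0.15 D

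**3. All randomised patients by arm, only recurrences by week 24 biopsied as polyp.** With a constant hazard over 48 weeks, the share recurring by week 24 is 1 − √(1 − p), where p is the 48-week rate.

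- p = 0.50: 1 − 0.707 = 0.293
- p = 0.20: 1 − 0.894 = 0.106
- p = 0.35: 1 − 0.806 = 0.194

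The differences are 0.293 − 0.106 = 0.187, about 0.19 D, and 0.293 − 0.194 = 0.099, about 0.10 D.

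**4. Illustration as a per-gene test.** Assume a within-tissue SD of 1, D of 1 or 2 SD, and a two-sided z-test at 0.05. For shares a and b with n per arm:

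z = D(a − b) / √{[2 + D²(a(1 − a) + b(1 − b))]/n}

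The chance of declaring an arm difference is Φ(z − 1.96) + Φ(−z − 1.96). The Houston number is not stated. I use n = 51 (half of the N = 102 scenario, all sites) and n = 17 (a third of that), both as assumptions.

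| Rates | n per arm | 48-week shares, D = 1 to 2 | Week-24 shares, D = 1 to 2 |
|---|---|---|---|
| 50% vs 20% | 51 | 0.28 to 0.61 | 0.14 to 0.32 |
| 50% vs 20% | 17 | 0.13 to 0.25 | 0.08 to 0.14 |
| 50% vs 35% | 51 | 0.10 to 0.19 | 0.07 to 0.12 |
| 50% vs 35% | 17 | 0.07 to 0.10 | 0.06 to 0.07 |

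Example, first row, 48-week shares, D = 1: z = 0.30/√[(2 + 0.25 + 0.16)/51] = 0.30/0.217 = 1.38, and the chance is 0.28.

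These are false positives only for a claim that the drug acts on the gene in mucosa. They are not false positives for a total effect that includes recurrence.

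**5. Same tissue in everyone.** The shares are equal, so the tissue-mix term is 0. Biopsy time would still differ by outcome.

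**The case against.** The strongest reply is that recurrence is itself an outcome of treatment. An arm comparison of all randomised Houston patients estimates a total effect on expression, fewer polyps included, and that is a fair reading of the stated aim. This stands. Such a comparison is valid, but it partly restates Aim 1 in terms of genes and cannot isolate action on mucosa. The illustrated contrast lacks even this protection, because its groups are selected on outcome.

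The illustration is only an example, and no analysis model is fixed. A reader might infer that Aim 2 is bound to report tissue differences as drug effects. The documents do not go that far: they merely contain nothing that prevents it.

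The single biopsy site might be thought to settle the matter. The two sections can be read together, one describing the state of the mucosa and the other the place, so a flat contradiction is not proven. But a common site limits only differences in location. It does not remove the polyp/non-polyp difference or the difference in time.

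Two further inferences should be resisted:

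- **ST2.** A reader might take ST2 and the other genes in the preliminary data to be especially exposed. The Objectives compare CRSwNP mucosa with healthy controls, not polyp with non-polyp mucosa within patients, so this is not shown.
- **Time on drug.** Adding the 3-week visit window to week 24 might suggest up to 27 weeks on drug. The course and the dispensed supply are 24 weeks. A later visit would be off drug.

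Finally, the predictive half of Aim 2 can rest on the surgical specimen, which is collected under one rule for all Houston patients. It need not be affected.

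**Conclusion.** The concern holds in a limited form. The post-treatment specimen depends on outcome in tissue type and in time, and the example contrast aligns drug, outcome and tissue, so tissue type alone could produce a difference of the full D. In an all-randomised arm comparison the tissue-mix part is about 0.10 to 0.19 D if only recurrences by week 24 are biopsied, and 0.15 to 0.30 D if all 48-week recurrences are.

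These figures rest on Table 2's rates holding at Houston, on a constant hazard for the week-24 range, and on the monitoring section's description of the tissue being followed. D is unknown, so the absolute size is too.

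The scope is an exploratory substudy at one site of a self-described pilot. The primary, secondary and safety endpoints are unaffected. The change is worth making because it is cheap and cannot be made once the specimens have been taken.

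**What to change.** 1. Reconcile the monitoring and biopsy sections so that every post-treatment biopsy comes from the same named site and, where accessible, from non-polyp mucosa, also in patients who recur.
2. State that recurrence after the week-24 biopsy does not replace that specimen.
3. Record tissue type, week and on/off-drug status for each specimen.
4. Base the drug-effect analysis on all randomised Houston patients by arm, using the specimen taken at recurrence or at week 24. Drop the contrast of itraconazole without recurrence against placebo with recurrence as evidence of a drug effect.
5. Use only the surgical specimen to identify predictive biomarkers.
6. Acknowledge that biopsy time still differs by outcome, up to about 24 weeks on drug. Report this as a limitation or adjust for it in a sensitivity analysis.

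**Cost.** Protocol wording for one site and three labels per specimen, with no added biopsy. The downside is that recurrent polyp tissue is not profiled for the drug-effect comparison. Where non-polyp mucosa cannot be reached in a patient who recurs, some tissue mix remains, and the recorded tissue type will show how much.
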